- b. **Procedures:** Participants will ~~provide breath CO~~, complete a timeline follow-back measure for the interim week which will query their use of study and non-study cigarettes, alcohol, marijuana, and alternative tobacco products. Participants will also complete a Health Changes Questionnaire to assess any adverse events, and the RA will follow-up on any ongoing medical events. [Note: These sessions were conducted virtually post-COVID.](#)

10. Week 4 Session

- a. **Purpose:** This laboratory session will evaluate end-point responses on behavioral economic measures and allow for collection of final biomarkers and cigarette collection.

Impact of nicotine reduction on adolescent cigarette use, alternative tobacco use, and harm from tobacco

PIs: [name] & [name]

b. Procedures: At the beginning of the session, participants will provide a breath CO sample, complete a timeline follow-back measure for the interim week which will query their use of study and non-study cigarettes, alcohol, marijuana, and alternative tobacco products. Female participants will provide a urine sample for a pregnancy test. Then, they will complete the cigarette purchase task (CPT), a behavioral economics-based measure of cigarette reinforcement, which assesses hypothetical demand for their usual brand and study cigarettes across a range of prices. Finally, they will complete the Experimental Tobacco Marketplace task again. Participants will also complete a Health Changes Questionnaire to assess any adverse events, and the RA will follow-up on and close any ongoing medical events. Should any adverse events be left open at this time, they will be re-assessed at the 30-day call. Participants will also complete an assessment of respiratory health and provide urine samples for biomarker assessment. Participants will also administer and anonymous debriefing survey which will ask them about the honest of their reporting. At the end of the week 4 session, following return of all products, participants will be debriefed on products used during the study. Health risk information will be presented for combusted cigarettes, e-cigs, and other tobacco products, using a handout drawn from CDC Fact Sheet.

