For the participant's protection, participants will be withdrawn immediately from the study if any of the following occur:

- 1) Cardiovascular disease (CVD) event: Typically includes MI (heart attack), PTCA (angioplasty/stenting), bypass surgery, stroke, peripheral vascular disease (arterial blockages in arms or legs leading to procedure or surgery). Less common CVD problems would be new cardiac arrhythmias (e.g., new atrial fibrillation) or new valvular disease (e.g., mitral or aortic regurgitation).
- 2) DVT/PE (deep vein thrombosis/pulmonary embolism, i.e., blood clots in the venous system).
- 3) Suicide Attempt: A participant will be withdrawn if he/she attempts suicide at any time during participation in the study.
- 4) Psychiatric Hospitalization: A participant will be withdrawn if he/she is hospitalized for psychiatric reasons at any time during participation in the study.
- 5) Pregnancy: If a participant indicates she is pregnant or has a positive pregnancy test at any session, she will be withdrawn from the study, and this event will remain open until delivery. At that time the license medical monitor will contact the participant to ask a few questions about the baby's health and will update the open 'Adverse Event Form'.

The following will be monitored and can lead to the participant being withdrawn by the PI or Licensed Medical Monitor:

- 1) Expired breath Carbon Monoxide >80 ppm
- 2) Any hospitalization or debilitation in which participation in the study could be detrimental to the recovery process. This will be self-reported by the participant and will

Impact of nicotine reduction on adolescent cigarette use, alternative tobacco use, and harm from tobacco

PIs: [name] & [name]

be reviewed by the MPIs and medical monitor to determine whether continued participation in the study is appropriate.

- 3) If a participant is behaving in an inappropriate or threatening manner, admits to lying about eligibility criteria, including omitting previous medical diagnoses and medications, is participating in other smoking research studies that could affect the primary outcome measures, does not follow study instructions, etc., then an MPI can withdraw him/her from the study at her discretion.

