Serious adverse events (SAEs): Information about all serious adverse events will be collected and recorded on a standard Serious Adverse Event Report Form. To ensure participant safety, each study-related serious adverse event will also be reported to the IRB office within 72 hours of learning of its occurrence. A serious adverse event is an undesirable sign, symptom or medical condition which:

1. is fatal or life-threatening
2. requires or prolongs hospitalization
3. results in persistent or significant disability/incapacity
4. constitutes a congenital anomaly or a birth defect
5. is medically significant, in that it may jeopardize the subject and may require medical or surgical intervention to prevent one of the outcomes listed above.

A hospitalization would not be considered to be a serious adverse event if it was elective, pre-planned, or for a pre-existing condition that did not worsen since starting the study; or for treatment on an outpatient basis for an event not fulfilling any of the definitions of serious given above and not resulting in hospital admission.

Any SAE occurring after the participant has signed the informed consent and until the participant has stopped study participation must be reported. Investigator responsibilities for notification of SAEs are described above.

c. Management of SAEs and Other Study Risks

The medical monitor will review all AEs. A study participant may be discontinued from the study if a medical monitor and/or an MPI determines it is the best decision in order to protect the safety of a participant. In the event that a participant either withdraws from the study or the investigator decides to discontinue a participant due to an AE/SAE, the participant will have appropriate follow-up medical monitoring. The participant experiencing an AE/SAE will be followed until the problem resolves, stabilizes, or is clearly unrelated to the study cigarettes. Any AE that remains open will be reviewed and closed during the 30-day follow-up phone call.

d. Medical Monitor Contact information:

[name]., Ph.D.

Email: [contact]

Impact of nicotine reduction on adolescent cigarette use, alternative tobacco use, and harm from tobacco

PIs: [name] & [name]

[contact]

[name]., R.N.P.

Email: [contact]

[contact]

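### Closing every open AE at the 30-day call contradicts keeping a pregnancy open until delivery, and the mandatory SAE window leaves a birth defect with no explicit SAE reporting duty

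*Protocol*

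**What the plan says.** The relevant rules are in Protocol sections 10 and 15.

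- **Week 4 session (section 10.b).** Of events still open at that visit: "Should any adverse events be left open at this time, they will be re-assessed at the 30-day call".
- **Withdrawal list (section 15.b).** "participants will be withdrawn immediately from the study if any of the following occur"; the list is cardiovascular event, DVT/PE, suicide attempt, psychiatric hospitalization and pregnancy. For pregnancy: "she will be withdrawn from the study, and this event will remain open until delivery". At delivery the medical monitor contacts her, asks about the baby and updates the Adverse Event Form, which is assumed still to be open.
- **SAE definition (section 15.b).** Criterion 4 is an event that "constitutes a congenital anomaly or a birth defect".
- **SAE window (section 15.b).** "Any SAE occurring after the participant has signed the informed consent and until the participant has stopped study participation must be reported".
- **SAE recording (section 15.b).** All SAEs go on the SAE Report Form, with no time limit in that sentence. Study-related SAEs go to the IRB within 72 hours, counted from when the study learns of them.
- **Management (section 15.c).** A participant with an AE or SAE "will be followed until the problem resolves, stabilizes, or is clearly unrelated to the study cigarettes". Shortly afterwards: "Any AE that remains open will be reviewed and closed during the 30-day follow-up phone call".

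**The concern.** The protocol gives staff incompatible instructions for the same record. One rule keeps a pregnancy open to delivery; another closes every open AE at a call that comes months earlier, with no exception. The closure sentence also sits in the same section as a rule that ties the end of follow-up to the state of the event and not to a date.

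Separately, the SAE window ends when participation stops. For a pregnancy, participation stops at withdrawal, so the outcome that criterion 4 describes arises after the window has shut. The protocol tests for pregnancy repeatedly (sections 4 and 11.b), so it anticipates the situation. At stake is whether a birth defect enters the SAE listing and the IRB report or only an AE form. The study population is adolescents, some of them minors.

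**Working it through.** The documents give no figure to reproduce. The check is a comparison of rules plus date arithmetic.

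**Step 1. When does an open AE end?** There are four answers:
- section 10.b: re-assessed at the 30-day call, with closure not mentioned;
- section 15.c, closure sentence: closed at that call, without condition;
- section 15.c, follow-up sentence: when it resolves, stabilizes or is clearly unrelated;
- section 15.b, pregnancy: at delivery.

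The closure sentence conflicts with the follow-up sentence for any event unresolved at the call, and with the pregnancy rule for any pregnancy that continues to delivery.

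**Step 2. Does the call always precede delivery?** Inputs from section 3: 7-day baseline (BL1 to BL2), 4-week experimental period, call 30 days after the end.
- Call, counted from BL2: 28 + 30 = 58 days, and 58 / 7 = 8.3 weeks.
- Call, counted from BL1: 7 + 28 + 30 = 65 days.

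The documents give no pregnancy timings, so two sets of assumptions are used.
- *Set A:* 40-week gestation, detected at 4 to 8 weeks, so delivery is 32 to 36 weeks after detection. If detected at BL2, closure is 8.3 weeks later and the gap from closure to delivery is 32 − 8.3 = 23.7 to 36 − 8.3 = 27.7 weeks. If detected at Week 4, closure is 30 / 7 = 4.3 weeks later and the gap is 27.7 to 31.7 weeks. Overall, about 24 to 32 weeks.
- *Set B (earliest case):* conception no more than 14 days before the negative screening test (day 0), delivery 22 to 38 weeks (154 to 266 days) after conception. Delivery is then no earlier than day 154 − 14 = 140 (very preterm) or day 266 − 14 = 252 (term). The gap after day 65 is at least 75 or 187 days.

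If the call is counted from an early withdrawal, it comes sooner and the gap grows. Under either set, closure precedes delivery.

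**Step 3. Is a birth defect inside the mandatory SAE window?** A positive test leads to immediate withdrawal. If withdrawal is what stops participation, the window closes then and delivery comes later. The delivery contact updates the Adverse Event Form; the SAE Report Form and the IRB report are not mentioned there. So the information is collected, but the duty to classify and report it as an SAE is not stated.

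**Step 4. The other mandatory withdrawals.** The cardiovascular event, DVT/PE, suicide attempt or psychiatric hospitalization happens before the withdrawal it causes, so it is inside the window and, if serious, must be reported. It is then followed under section 15.c. Only a new serious event after withdrawal falls outside the mandatory window.

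**The case against.** A reader might infer that a birth defect can never be captured, or that capture of criterion 4 is nil. The documents do not support that. Section 15.b plans a contact at delivery specifically about the baby's health, with an update to the AE record. The window sentence says what must be reported and does not forbid later reporting. The recording sentence covers all SAEs without a time limit, and the 72-hour clock runs from knowledge, so a study-related anomaly learned of at delivery could be reported under it.

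A reader might also infer that the SAE listing would miss the events that force withdrawal. Step 4 shows otherwise. A later death or readmission may also be the course of an event already under follow-up.

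Three further arguments have some force. The specific pregnancy rule can be read as an exception to the general closure sentence; that is sensible, but the text does not say so. The point at which participation has stopped is not defined, and the protocol prescribes contact after withdrawal, so the window could be read as longer; that is a reason to define it. Finally, the SAP, dated 9/1/23, describes the analyses in the past tense, so an amendment may come too late to change much data collection.

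What remains is that one closing rule contradicts two others as written, and that SAE reporting of a listed criterion depends on which sentence staff follow.

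**Conclusion.** The concern holds in a limited form. For any pregnancy that continues to delivery, the open-until-delivery rule and the 30-day closure rule cannot both be applied. The closure sentence likewise conflicts with the follow-up rule in its own section for any event unresolved at the call. On a plain reading, a birth defect would be learned of and noted on the AE form, with no explicit duty to report it as an SAE. A new serious event after another mandatory withdrawal is in the same position, although the event that caused the withdrawal is not.

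The order of call and delivery is secure; the length of the gap rests on the assumed timings in Step 2. The window conclusion rests on reading withdrawal as the end of participation. The documents give no event rate, but in a sample planned at 120 few such events are expected. No outcome, analysis or power figure is affected. This is an inconsistency in safety reporting that should be corrected.

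**What to change.** Reconcile sections 10.b, 15.b and 15.c:

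1. Reword the closure sentence so that open AEs are reviewed at the 30-day call and closed only if the follow-up rule in section 15.c is met, with pregnancies staying open to delivery as section 15.b already provides. Align the Week 4 sentence with this.
2. Define when participation stops for SAE reporting, and state that the mandatory window includes the follow-up already planned after withdrawal: the 30-day safety call and the delivery contact. Confirm that the call applies to withdrawn participants, because sections 3 and 12 do not say so.
3. State that a birth defect learned of at the delivery contact goes on the SAE Report Form as well as the AE form.

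The withdrawal criteria are unchanged. The cost is a wording amendment and possibly a few late SAE reports. The delivery contact is already planned, and so is the call, subject to the confirmation in item 2.

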Cover page for Data Analysis Plan

NCT03860077

Grant number: R01DA047356

Grant Title: Impact of Nicotine Reduction on Adolescent Cigarette Use, Alternative Tobacco Use, and
Harm From Tobacco

Document date: 9/1/23

Data Analytic Approach and Power.

Overview and justification. Mixed effects models evaluated change in total cigarette use, alternative tobacco product use, study cigarette use, and biomarkers of nicotine exposure from baseline to the final study week. All analyses were with SAS V9.4 software (SAS Institute Inc., Cary, NC, USA, 2016). Due to data-collection disruptions related to the COVID-19 pandemic and intermittent data-collection challenges with the ecological momentary assessment (EMA) program, we elected to utilize the most complete data stream for primary analyses, which was Time Line Follow Back (TLFB) of outcomes collected at Week 4 and Baseline. Consistent with our prior work (e.g., ¹), aggregated timeline follow-back (TLFB) data from the final week of study cigarette use (i.e., Week 4) was compared to a one-week baseline period during which participants used usual brand cigarettes (i.e., Baseline). The mixed effect model using TLFB data was chosen over other possible analytic approaches (e.g., ANCOVA with baseline outcome covariates) to reduce bias stemming from (1) pre-randomization group differences in baseline outcome levels, and (2) missing outcome data.

Analyses to address project aims. To address primary aims, 2-group (VLNC & NNC) x 2 repeated measures (Baseline & Week 4) mixed effects models tested the effect of the randomization group (VLNC vs. NNC) on change in cigarette use and alternative tobacco product (ATP) use from Baseline to Week 4. Similarly, to address secondary aims related to biomarkers of nicotine exposure, 2 x 2 mixed models tested the effects of VLNC vs. NNC cigarettes on change in biomarkers of nicotine exposure (i.e., total nicotine equivalents [TNEs] and cotinine), as well as average number study cigarettes smoked per day relative to average number of usual brand cigarettes smoked per day. In all models, Group (VLNC = 1; NNC = 0) was a between-subjects predictor, and Time (Baseline vs. Week 4) was the repeated measure. Subject was treated as a random effect to account for subject-level differences in baseline outcome levels. The focal tests evaluated the difference in change from Baseline to Week 4 (i.e., Time) in the VLNC vs. NNC condition (i.e., Group), which is a cross-level interactive effect of Time and Group. A *p*-value < 0.05 was interpreted as meeting statistical significance criteria. For all estimation

parameters, we report effect estimates, standard errors, and 95% confidence intervals in addition to p values.

Consistent with the original statistical analysis plan, demographics and baseline data on participant tobacco use history and individual characteristics were summarized using univariate descriptive statistics (e.g., means, standard deviations, frequencies). Data visualization and formal statistical evaluation of means, standard deviations, skewness, and kurtosis, assessed the distributional characteristics of each outcome. Where the assumptions of models implementing a normal (Gaussian) outcome distribution were not met, the statistical approach was revised accordingly. The following analytic procedures were required to meet model assumptions and account for skewed outcome distributions and low frequency events for certain outcomes.

1. Average cigarettes per day was positively skewed, with a non-normal residual distribution in a mixed model analysis specifying a normal (Gaussian) outcome distribution. Therefore, this outcome was recoded to integers and modeled as a count with a negative binomial distribution and log link.
2. Frequencies of alternative product use (ATP) were low, particularly for combustible ATP use. Therefore, for the primary ATP outcome, combustible and non-combustible ATP use were modeled jointly and recoded as a dichotomous outcome (0 = <7 combined days of ATP use; 1 = 7+ combined days of ATP use), with a binary distribution and log link.
3. As secondary outcomes and to evaluate sensitivity, combustible and non-combustible ATP use were also considered independently as separate outcomes. Frequencies of combustible ATP use at Week 4 were too low to allow for model convergence. Frequencies of non-combustible alternative product use (ATP) were bimodal with peaks at 0 (no use) and 7 (daily use). Therefore, this outcome was recoded as a dichotomous outcome (0 = non-daily non-combustible ATP use; 1 = daily non-combustible ATP use) with a binary distribution and log link.
4. The study cigarette secondary outcome was modeled with a normal, Gaussian distribution. Baseline (Time = 0) in this analysis was average number of usual brand cigarettes at baseline,

prior to randomization, and Week 4 (Time = 1) was the average number of study cigarettes at Week 4.

5. Biomarker outcomes (i.e., total nicotine equivalents [TNEs] and cotinine) were modeled with normal, Gaussian distributions.

Missing data and sample size considerations. Missing data were assumed missing-at-random² (Whittaker, Pituch, & McDougall, 2014). Under the missing-at-random assumption, missing data for each focal variable is not expected to be related to that variable itself, e.g., a missed outcome assessment was not related to what that value would have been if it were assessed³ (Enders, 2006). The mixed model approach utilizing SAS software implemented restricted maximum likelihood estimation (continuous outcomes) and pseudolikelihood estimation (count and binary outcomes) to account for missing data. The mixed model reduces bias relative to other common approaches, particularly in cases where Group size is unbalanced due to attrition and/or baseline outcome levels differ between randomization groups.

Original power analyses suggested a target sample size of 120 participants (60 per Group) yielded sufficient power to detect effects of Group (VLNC vc. NNC) on change in cigarettes smoked and alternative products used, as measured via ecological momentary assessment (EMA). Specified population parameter estimates were based on prior literature^{4,5} and previous studies¹, and power was calculated to reflect a small to medium effect of VLNC vs. NNC on continuous (i.e., normally distributed) outcomes. For the direct effect of Group on primary outcomes, power to detect a small to medium direct effect (estimate = .15) with 120 participants (60 per Group) was .74 with 95% coverage, where power to detect a slightly larger effect (estimate = .20) was .96, with 95% coverage. Due to unforeseeable effects of the COVID-19 pandemic on data collection and unanticipated, intermittent challenges with the EMA software, the total number of participants was reduced, as was the degree of complete EMA data. As such, TLFB were utilized for an intent-to-treat analysis, thereby retaining all participants who provided Baseline outcome data.

1. [name] RN, Tidey JW, Jackson KM, et al. The Impact of Reducing Nicotine Content on Adolescent Cigarette Smoking and Nicotine Exposure: Results from a Randomized Controlled Trial. *Nicotine Tob Res Off J Soc Res Nicotine Tob*. Published online December 9, 2022:ntac279. doi:10.1093/ntr/ntac279
3. Enders CK. A primer on the use of modern missing-data methods in psychosomatic medicine research. *Psychosom Med*. 2006;68(3):427-436. doi:10.1097/01.psy.0000221275.75056.d8

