- d. **Informed consent procedure:** Adolescents who meet initial eligibility criteria, and who remain interested after hearing a more detailed description of the study, will provide contact information for their parent or legal guardian (minors only) so that parental informed consent can be obtained; 18-19 year olds can provide their own informed consent (see **18+ Consent** attachment). Research staff will call the minor's parent/guardian and provide the study information and answer any questions that they have (see **Parent Phone Script** attachment). If parents are willing to consent to their child's participation, we will mail or email them a consent form to sign (and one to keep), which the adolescent participant will bring to the first session (see **Parental Consent** attachment). Eligible interested adolescents (with verbal parental consent if minors) will be scheduled for the initial in-person session and transportation arranged if necessary (see **Adolescent Assent** attachment).

4. Screening

- a. During the initial in-person screening, participants will complete several questionnaires and have their CO taken to confirm eligibility to enroll. Female participants will also submit a urine sample to test for pregnancy. Urine will be sampled for cotinine levels if necessary. The Timeline Follow back, stages of change, and MINI suicide subscale will be used to determine eligibility. We estimate that we may need to consent up to 200 adolescents to result in a final sample of N=120.

b. Inclusion Criteria

- 1) Ages 15-~~19~~20 inclusive
- 2) Male and female current daily smokers
 - a. Defined as self-reported daily cigarette smoking at phone screening AND

Impact of nicotine reduction on adolescent cigarette use, alternative tobacco use, and harm from tobacco

PIs: [name] & [name]

- b. a breath carbon monoxide (CO) criterion of 5 ppm or higher; if this is not met, urine cotinine levels, detected by a NicAlert cotinine screening device, must indicate recent smoking (level 3 or higher)
- 3) Current users of alternative tobacco product(s)
 - a. Defined as any self-reported use of at least one non-cigarette tobacco product (e.g., e-cigarettes, little cigars, cigarillos, hookah, etc.) in the past 30 days
- 4) Participants must speak and comprehend English well enough to complete study procedures.
 - a. Participant will be asked to read aloud first few lines of informed consent and then summarize the contents aloud to check for competency

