- a. **Purpose:** This check-in visit can occur either at our research lab or in the community at the participant's preference and convenience. The purpose of this check-in is to check on safety/any adverse events, ~~check CO level~~, and dispense product; allowing participants to meet us in the community will help reduce the burden of travel time for participants and is designed to reduce study attrition, particularly among participants for whom the logistics of scheduling and transportation may be challenging.
- b. **Procedures:** Participants will ~~provide breath CO~~, complete a timeline follow-back measure for the interim week which will query their use of study and non-study cigarettes, alcohol, marijuana, and alternative tobacco products. Participants will also complete a Health Changes Questionnaire to assess any adverse events, and the RA will follow-up on any ongoing medical events. [Note: These sessions were conducted virtually post-COVID.](#)

8. Week 2 Laboratory Session

- a. **Purpose:** This laboratory session will evaluate mid-point responses to study cigarettes.
- b. **Procedures:** At the beginning of the session, participants will provide a breath CO sample, complete a timeline follow-back measure for the interim week which will query their use of study and non-study cigarettes, alcohol, marijuana, and alternative tobacco products, and complete measures of craving (QSU), withdrawal (MNWS) and mood (PANAS). Female participants will provide a urine sample for a pregnancy test. They will then smoke one of their study cigarettes. Next, they will provide a post-smoking CO sample, repeat the QSU, MNWS, and PANAS, and then complete measures of cigarette subjective effects (CES). Participants will also complete a Health Changes Questionnaire to assess any adverse events, and the RA will follow-up on any ongoing medical events.

9. Week 3 Safety & Product Dispensation Check-In

- a. **Purpose:** As described above (Week 1 Check-In), this check-in visit can occur either at our research lab or in the community; the purpose is to check on safety/any adverse events, ~~check CO~~, and dispense product.

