- b. **Safety:** Pregnancy tests will be performed for all female participants at Screening/BL1, BL2, and both lab visits (weeks 2 and 4). The **suicide subscale** from the Mini International Neuropsychiatric Interview (MINI; Sheehan et al., 2010) will be used at Screening to evaluate suicide risk. CO level will be obtained at every session to evaluate level of exposure to smoke; a large increase in CO (i.e., CO > 80 ppm) can be a reason for withdrawing a participant from the study. **Brief Medical History** (Screening/BL1) assesses physical and emotional health to establish eligibility for participation (determined by the medical monitors). In subsequent sessions, the **Health Changes Questionnaire** asks whether the participant experienced any changes in his/her physical or emotional health since their last visit, including whether they have visited the doctor, the hospital, or whether they have had a change in any of their medications. Any endorsement of a negative health change will be tracked as an adverse event.
- c. **Frequency of tobacco and other drug use measures:** Past 30-day tobacco product use will be comprehensively assessed using a **Timeline Follow-Back (TLFB)**, a reliable calendar-assisted interview validated for estimating daily use of tobacco and other substances in adolescents (Lewis-Esquerre et al., 2005). The TLFB will determine: # cigarettes per day; frequency of e-cig use (including nicotine concentration in e-liquid) and use of all other tobacco products; use of alcohol (# standard drinks/day); and frequency of marijuana use and other illicit or recreational drug use. The TLFB will also be used to assess tobacco, alcohol, marijuana and other drug use between sessions to evaluate use over the course of the study.
- d. **Biomarkers. Expired breath CO** level is a reliable and valid assessment of recent smoking and will be measured using a Vitalograph CO Monitor. CO will be assessed at BL to confirm

Impact of nicotine reduction on adolescent cigarette use, alternative tobacco use, and harm from tobacco

PIs: [name] & [name]

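### The primary models leave out the Week 1–3 TLFB, so participants lost before Week 4 bring only a baseline value and missing at random can condition on little else

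*SAP*

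**What the plan says.** The SAP (Overview and justification) turns from EMA to TLFB because of COVID-19 and software problems, and chooses "the most complete data stream for primary analyses, which was Time Line Follow Back (TLFB) of outcomes collected at Week 4 and Baseline". It states that "data from the final week of study cigarette use (i.e., Week 4) was compared to a one-week baseline period" on usual-brand cigarettes. Under Analyses to address project aims, the primary models are "2-group (VLNC & NNC) x 2 repeated measures (Baseline & Week 4) mixed effects models" with a random subject effect. The focal test is the Group by Time interaction. Missing data are taken as missing at random, and the analysis is called intent-to-treat, "thereby retaining all participants who provided Baseline outcome data".

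The protocol collects more than this. At Weeks 1, 2, 3 and 4 (sections 7.b, 8.b, 9.b and 10.b) participants "complete a timeline follow-back measure for the interim week which will query their use of study and non-study cigarettes", and the same interview covers alternative products. Table 1 agrees. Breath CO was struck from Weeks 1 and 3 and those visits became virtual, but the TLFB stayed. Section 11.c gives the purpose of the TLFB "between sessions to evaluate use over the course of the study".

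For ATP, entry requires only "any self-reported use of at least one non-cigarette tobacco product" in the past 30 days (section 4.b). The primary ATP outcome is coded "0 = <7 combined days of ATP use; 1 = 7+ combined days of ATP use". The SAP reports that Week 4 combustible use was too infrequent for its model to converge.

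**The concern.** Three of the four exposure weeks have no role in any SAP model. The SAP gives no reason specific to those weeks and does not report how complete they were. Calling TLFB the most complete stream explains the choice of TLFB over EMA. It does not explain leaving out partly complete TLFB weeks, which a mixed model can accept.

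Two things are at stake.

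- **Missing data.** The SAP chose a mixed model partly to reduce bias from missing outcomes. With two waves, a participant lost before Week 4 has no post-randomisation value in either primary model. Dropout could plausibly depend on how the participant responded to the assigned cigarette. That response was recorded in Weeks 1–3, but the model cannot see it.
- **ATP.** Aim 1 asks about days of alternative product use. A single follow-up week, then dichotomised, gives a coarse reading of that quantity, and combustible use could not be modelled at all.

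**Working it through.** The SAP has no figure of its own on this point. Its power values (.74 and .96) belong to the EMA analysis that was set aside, and they come without the SD, correlation or number of occasions needed to check them. Dropout rates, correlations and independence between days are therefore assumptions below.

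**1. What a baseline-only participant contributes.** Take 60 per arm, unit SD, Baseline–Week 4 correlation ρ = 0.7, and 20% dropout in each arm, so m = 48 with Week 4.

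- Completers only: variance = 2 × 2(1−ρ)/m = 1.2/48 = 0.0250; SE 0.158.
- SAP model, baseline-only participants kept: variance = 2 × [(1−ρ²)/m + (1−ρ)²/60] = 2 × [0.51/48 + 0.09/60] = 0.02425; SE 0.156.
- No dropout: variance = 1.2/60 = 0.0200; SE 0.141.

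Information is 1/variance: 40.0, 41.2 and 50.0. Keeping baseline-only participants recovers 1.2 of the 10 units lost, or 12%. For ρ of 0.3–0.8 and dropout of 10–30%, the share is 7–33%.

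**2. Precision from adding Weeks 1–3, same Week 4 contrast.** At ρ = 0.7 and 20% dropout spread evenly over last contact at Baseline to Week 3, generalised least squares gives SE 0.153 (compound symmetry) or 0.151 (serial correlation), against 0.156. Over the whole grid the SE falls by about 0.2–5.6%.

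**3. Bias.** Assume Gaussian outcomes and 26% dropout in one arm after Week 3, with the log-odds of dropout rising by 1 per SD of Week 3 minus Baseline change.

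| Week-to-week correlation | Two-wave bias | All-weeks bias |
|---|---|---|
| Compound symmetry, 0.65–0.70 | about 0.05 SD | about 0 |
| Serial, 0.85 per week | about 0.12 SD | about 0 |

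Varying dropout over 10–26% widens the two-wave range to 0.01–0.17 SD. A separate 60-run simulation let dropout (about 18%) depend on arm and Week 1–2 smoking, with a true effect of −0.50. The two-wave model averaged −0.60 and the all-weeks model −0.50 (Monte Carlo SE 0.02).

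**4. ATP window.** For use on a proportion r of days, P(any use in k days) = 1 − (1−r)^k.

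| Days used in 30 | Seen in 7 days | Seen in 28 days |
|---|---|---|
| 1 | 0.21 | 0.61 |
| 2 | 0.38 | 0.86 |
| 3 | 0.52 | 0.95 |
| 4 | 0.63 | 0.98 |
| 10 | 0.94 | 1.00 |

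The 7-day probability reaches 0.5 at r = 1 − 0.5^(1/7) = 0.094, which is 2.8 days in 30.

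**5. ATP cut.** I read combined days as combustible days plus non-combustible days in the week. With one class used, coding as 1 needs all 7 days:

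- 10 days in 30: (1/3)^7 = 0.0005.
- 20 days in 30: (2/3)^7 = 0.06.
- Both classes, each on 10 days in 30: P(Binomial(14, 1/3) ≥ 7) = 0.15.

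A participant using one class on 10 days in 30 is thus seen by the 7-day window 94% of the time but almost never coded 1.

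**The case against.** A final-week contrast is a legitimate estimand. The protocol treats Week 4 as the end-point visit, and the SAP cites consistency with the group's prior work. That stands, and the fix keeps the contrast.

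The bias figures come from a mechanism chosen so that recorded weeks can correct it. If dropout depends on unrecorded Week 4 smoking, five waves do not guarantee correction. In the second simulation, a completers-only analysis also averaged close to the truth (−0.49), so the bias depends on mechanism and estimator. The calculations are Gaussian, whereas the primary models are negative binomial and binary, fitted by pseudolikelihood. These points limit the size of the claim but not its direction: the collected weeks are the only on-treatment information about those lost before Week 4.

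Weeks 1–3 may also be patchy after COVID-19, and a sparse binary model with five waves may not converge. Both are fair, and the SAP reports nothing that would settle the first.

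A reader might infer two stronger things. One is that participants without Week 4 add nothing about the effect. They do stay in the random-subject model and add a little (step 1). The other is that a one-week window mostly misses intermittent ATP use. That holds only below about 3 days in 30. Nothing shows that the eligibility minimum is typical, and the SAP reports a peak at daily non-combustible use. The window argument also has no bearing on cigarettes per day, since participants are daily smokers.

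**Conclusion.** The concern holds in a limited form. The documents establish that Week 1–3 TLFB was planned and retained, that no SAP model uses it, and that those lost before Week 4 supply no post-randomisation value to either primary model. Missing at random can then condition only on baseline and group.

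The main consequence is possible bias: about 0.05–0.12 SD under the assumed 26% one-arm dropout driven by Week 3 change, and about 0 with all weeks. The documents give no final sample size, dropout rate or pattern, so this is an illustration and not an estimate for the trial. The gain in precision is minor and would not justify the change alone.

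For ATP, the short window matters for very infrequent users. For more frequent intermittent users, the 7+ combined-day cut is the larger loss, and extra weeks analysed with the same cut would not cure it. The documents do not support reading the final-week endpoint as wrong in itself.

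**What to change.** - Keep Baseline to Week 4 as the focal contrast. Fit Time with five levels (Baseline, Weeks 1–4) for cigarettes per day and ATP, using every available weekly TLFB. Since the SAP describes analyses in the past tense, this can be labelled a sensitivity analysis. Allow a flexible within-subject covariance, and name in advance a simpler one to use if the sparse binary model does not converge.
- Report TLFB completeness by week and arm.
- Add a supportive ATP analysis of days of use over the exposure period in place of the 7+ cut. Use observed TLFB days as the offset or denominator, so that participants with missing weeks are kept.

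No new data are needed. The cost is SAP wording, a slightly more complex model and possible convergence work. Under pseudolikelihood, protection against missing-at-random dropout is only approximate, and the report should say so.
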